3.1.3.2. Treatment Group B

3.1.3.2.1. Treatment Group B Dose Expansion Cohorts (Part 1)

Because higher doses of epigenetic priming regimens may be deleterious to immune function, expansion cohorts at each dose level tested that cleared the DLT window will be opened for signal detection [REDACTED] analysis to guide an RP2D. Once an RP2D is determined, this dose will be used in Part 2 in the Simon 2-stage and treatment sequencing tumor biopsy cohorts. During dose expansion, 5 NSCLC subjects who progressed on a PD-1 pathway–targeted agent and 5 MSS CRC subjects will be enrolled at each dose level with DLT clearance as detailed below.

The expansion will include:

1. Safety/efficacy cohorts in NSCLC (2 tumor biopsies are required)
 - a. B-1: INCB057643 4 mg QD followed by the pembrolizumab/epacadostat doublet
 - b. B-3: INCB057643 8 mg QD followed by the pembrolizumab/epacadostat doublet
 - c. B-5: INCB057643 12 mg QD followed by the pembrolizumab/epacadostat doublet
2. Safety/efficacy cohorts in MSS CRC (2 tumor biopsies are required)
 - a. B-2: INCB057643 4 mg QD followed by the pembrolizumab/epacadostat doublet
 - b. B-4: INCB057643 8 mg QD followed by the pembrolizumab/epacadostat doublet
 - c. B-6: INCB057643 12 mg QD followed by the pembrolizumab/epacadostat doublet

The following cohorts will be expanded only under certain circumstances, as listed below:

1. Cohorts B-1 and B-2: Objective responses have been seen in subjects dosed with INCB057643 at 8 and 12 mg QD and, as such, are known PADs. However, 4 mg QD dosing has not been evaluated in humans. To ensure 4 mg QD is a PAD, Cohorts B-1 and B-2 will only be enrolled if $\geq 1/3$ of the subjects in the dose-escalation cohort have a 25% drop in platelet count from Cycle 1 Day 1 to Cycle 2 Day 1.

Continuous evaluation of toxicity events will be performed throughout the expansion cohorts. After the dose-expansion cohorts have been enrolled, beginning with the sixth patient for a specific regimen, if $> 40\%$ of subjects have an AE \geq Grade 3 that is attributable to the investigational agents, further enrollment of subjects will be suspended until the sponsor, investigators, and regulatory authorities (if applicable) have determined the appropriate course of action. If an expansion cohort is discontinued because of toxicity, a new cohort may be initiated at a previously tested lower dose level.

Following completed enrollment of the safety/efficacy expansion cohorts, there will be an optional 8-week pause to utilize [REDACTED] data for RP2D determination. During this time period, no subject enrollment may be allowed. If there is no evidence of clinical efficacy [REDACTED] in the dose-expansion cohorts, enrollment in the respective treatment group will be stopped prior to Part 2.

3.1.3.2.2. Treatment Group B Simon 2-Stage Cohorts (Part 2)

Following safety, efficacy, [REDACTED] data evaluation, an RP2D will be determined. A Simon 2-stage design will be used with a stopping rule to allow for early termination of a particular cohort at the end of Stage 1 if there are insufficient responses observed. During Stage 1, 8 NSCLC subjects who progressed on a PD-1 pathway-targeted agent and 8 MSS CRC subjects will be enrolled. If no responses are observed in the NSCLC PD-1 failure and MSS CRC cohorts, the cohort(s) will be discontinued. If at least 1 response is observed in the NSCLC PD-1 failure or MSS CRC cohort, 19 additional NSCLC PD-1 failure or MSS CRC subjects will be enrolled (Stage 2), for a maximum of 27 subjects per cohort (see [Table 6](#)).

Table 6: Treatment Group B Safety/Efficacy Expansion Cohorts (Part 2)

Cohort	Treatment	Tumor Type (n)
Expansion Cohort B-7	MTD, maximum tested dose, or PAD for the INCB057643 + pembrolizumab + epacadostat combination.	A maximum of 27 subjects with previously treated Stage IV or recurrent NSCLC with progression on a prior PD-1 pathway-targeted agent.
Expansion Cohort B-8	MTD, maximum tested dose, or PAD for the INCB057643 + pembrolizumab + epacadostat combination.	A maximum of 27 subjects with previously treated Stage IV MSS CRC.

3.1.3.2.3. Treatment Group B Treatment Sequencing Tumor Biopsy Cohorts (Part 2)

The sequencing biopsy cohorts require 3 tumor biopsies (except for Cohort B-11, which requires 2 tumor biopsies) to identify epigenetic changes and changes in the tumor microenvironment induced by each of the components of the regimen. All subjects will have tumor biopsies at baseline and 2 additional biopsies while on study treatment.

If Stage 1 is passed in Cohort B-7 or B-8, approximately 25 subjects will be enrolled in Expansion Cohorts B-9, B-10, and B-11. The eligible tumor types for Expansion Cohorts B-9, B-10, and B-11 are HNSCC, melanoma, UC, and MSS CRC. In Expansion Cohorts B-9, B-10, and B-11, subjects with tumor types other than MSS CRC must have had disease progression on a prior PD-1 pathway-targeted agent.

Five to 8 evaluable subjects per tumor type in Expansion Cohorts B-9, B-10, and B-11 will initiate treatment and have tumor biopsies performed as indicated in [Table 7](#).

Table 7: Treatment Group B Treatment Sequencing Tumor Biopsy Cohorts (Part 2)

Cohort	Treatment Sequence	Biopsy Sequence	Tumor Type (n)
Expansion Cohort B-9	INCB057643 continuous monotherapy during C1, initiate pembrolizumab and epacadostat on C2D1 after biopsy #2.	Biopsy #1 at baseline. Biopsy #2 on C2D1 (window C1D15 to C2D1, biopsy before pembrolizumab/ epacadostat administration). Biopsy #3 during Week 8 or 9.	HNSCC (5-8) Melanoma (5-8) UC (5-8) MSS CRC (5-8)
Expansion Cohort B-10	INCB057643 and epacadostat for 1 cycle, initiate pembrolizumab after biopsy #2.	Biopsy #1 at baseline. Biopsy #2 on C2D1 (window C1D15 to C2D1, biopsy before pembrolizumab administration). Biopsy #3 during Week 8 or 9.	HNSCC (5-8) Melanoma (5-8) UC (5-8) MSS CRC (5-8)
Expansion Cohort B-11	INCB057643, epacadostat, and pembrolizumab beginning C1.	Biopsy #1 at baseline. Biopsy #2 during Week 5 or 6.	HNSCC (5-8) Melanoma (5-8) UC (5-8) MSS CRC (5-8)

The sponsor will manage enrollment so that there are 5 to 8 evaluable subjects for a given tumor type. Subjects may be replaced if they have not completed all of the biopsy requirements.

3.1.3.3. Treatment Group C

3.1.3.3.1. Treatment Group C Dose Expansion Cohorts (Part 1)

Because higher doses of epigenetic priming regimens may be deleterious to immune function, expansion cohorts at each dose level tested that clear the DLT window will be opened for signal detection [REDACTED] analysis to guide an RP2D. Once an RP2D is determined, this dose will be used in Part 2 in the Simon 2-stage and treatment sequencing tumor biopsy cohorts. During dose expansion, 5 NSCLC subjects who progressed on a PD-1 pathway-targeted agent and 5 MSS CRC subjects will be enrolled at each dose level with DLT clearance as detailed below.

The expansion will include:

1. Safety/efficacy cohorts in NSCLC (2 tumor biopsies are required)
 - a. C-1: INCB059872 1 mg QoD followed by the pembrolizumab/epacadostat doublet
 - b. C-3: INCB059872 2 mg QoD followed by the pembrolizumab/epacadostat doublet
 - c. C-5: INCB059872 1 mg QD followed by the pembrolizumab/epacadostat doublet
 - d. C-7: INCB059872 3 mg QoD followed by the pembrolizumab/epacadostat doublet
2. Safety/efficacy cohorts in MSS CRC (2 tumor biopsies are required)
 - a. C-2: INCB059872 1 mg QoD followed by the pembrolizumab/epacadostat doublet
 - b. C-4: INCB059872 2 mg QoD followed by the pembrolizumab/epacadostat doublet
 - c. C-6: INCB059872 1 mg QD followed by the pembrolizumab/epacadostat doublet
 - d. C-8: INCB059872 3 mg QoD followed by the pembrolizumab/epacadostat doublet

The following cohorts will be expanded only under certain circumstances, as listed below:

1. Cohorts C-1, C-2, C-5, and C-6: Objective responses have been seen in subjects dosed with INCB059872 2 and 3 mg QoD and above and, as such, are PADs. However, 1 mg QoD has not been evaluated in humans, and there is no objective data to show that 1 mg QD is a PAD. To ensure that 1 mg QD and 1 mg QoD are PADs, Cohorts C-1, C-2, C-5, and C-6 will only be enrolled if $\geq 1/3$ of the subjects in the dose-escalation cohorts have a 25% drop in platelet count from Cycle 1 Day 1 to Cycle 2 Day 1.
2. Cohorts C-3 and C-4 will only be expanded if both of the following occur:
 - a. The INCB059872 1 mg QD cohort does not clear its DLT window or is deemed not tolerated for reasons outside of strict DLT criteria.
 - b. The INCB059872 2 mg QoD cohort clears its DLT window and is deemed to have acceptable tolerability.

Continuous evaluation of toxicity events will be performed throughout the expansion cohorts. After the dose-expansion cohorts have been enrolled, beginning with the sixth patient for a specific regimen, if > 40% of subjects have an AE \geq Grade 3 that is attributable to the investigational agents, further enrollment of subjects will be suspended until the sponsor, investigators, and regulatory authorities (if applicable) have determined the appropriate course of action. If an expansion cohort is discontinued because of toxicity, a new cohort may be initiated at a previously tested lower dose level.

Following completed enrollment of the safety/efficacy expansion cohorts, there will be an optional 8-week pause to utilize [REDACTED] data for RP2D determination. During this time period, no subject enrollment may be allowed. If there is no evidence of clinical efficacy [REDACTED] in the dose-expansion cohorts, enrollment in the respective treatment group will be stopped prior to Part 2.

3.1.3.3.2. Treatment Group C Simon 2-Stage Cohorts (Part 2)

Following safety, efficacy, [REDACTED] data evaluation, an RP2D will be determined. A Simon 2-stage design will be used with a stopping rule to allow for early termination of a particular cohort at the end of Stage 1 if there are insufficient responses observed. During Stage 1, 8 NSCLC subjects who progressed on a PD-1 pathway-targeted agent and 8 MSS CRC subjects will be enrolled. If no responses are observed in the NSCLC PD-1 failure and MSS CRC cohorts, the cohort(s) will be discontinued. If at least 1 response is observed in the NSCLC PD-1 failure or MSS CRC cohort, 19 additional NSCLC PD-1 failure or MSS CRC subjects will be enrolled (Stage 2), for a maximum of 27 subjects per cohort (see [Table 8](#)).

Table 8: Treatment Group C Safety/Efficacy Expansion Cohorts (Part 2)

Cohort	Treatment	Tumor Type (n)
Expansion Cohort C-9	MTD, maximum tested dose, or PAD for the INCB059872 + pembrolizumab + epacadostat combination.	A maximum of 27 subjects with previously treated Stage IV or recurrent NSCLC with progression on a prior PD-1 pathway-targeted agent.
Expansion Cohort C-10	MTD, maximum tested dose, or PAD for the INCB059872 + pembrolizumab + epacadostat combination.	A maximum of 27 subjects with previously treated Stage IV MSS CRC.

3.1.3.3.3. Treatment Group C Treatment Sequencing Tumor Biopsy Cohorts (Part 2)

The sequencing biopsy cohorts require 3 tumor biopsies (except for Cohort C-13, which requires 2 tumor biopsies) to identify epigenetic changes and changes in the tumor microenvironment induced by each of the components of the regimen.

If Stage 1 is passed in Cohort C-9 or C-10, approximately 25 subjects will be enrolled in Expansion Cohorts C-11, C-12, and C-13. The eligible tumor types for Expansion Cohorts C-11, C-12, and C-13 are HNSCC, melanoma, UC, and MSS CRC. In Expansion Cohorts C-11, C-12, and C-13, subjects with tumor types other than MSS CRC must have had disease progression on a prior PD-1 pathway–targeted agent.

Five to 8 evaluable subjects per tumor type in Expansion Cohorts C-11, C-12, and C-13 will initiate treatment and have tumor biopsies performed as indicated in [Table 9](#).

Table 9: Treatment Group C Treatment Sequencing Tumor Biopsy Cohorts (Part 2)

Cohort	Treatment Sequence	Biopsy Sequence	Tumor Type (n)
Expansion Cohort C-11	INCB059872 continuous monotherapy during C1, initiate pembrolizumab and epacadostat on C2D1 (after biopsy #2).	Biopsy #1 at baseline. Biopsy #2 on C2D1 (window C1D15 to C2D1, biopsy before pembrolizumab/epacadostat administration). Biopsy #3 during Week 8 or 9.	HNSCC (5-8) Melanoma (5-8) UC (5-8) MSS CRC (5-8)
Expansion Cohort C-12	INCB059872 and epacadostat for 1 cycle, initiate pembrolizumab after biopsy #2.	Biopsy #1 at baseline. Biopsy #2 on C2D1 (window C1D15 to C2D1, biopsy before pembrolizumab administration). Biopsy #3 during Week 8 or 9.	HNSCC (5-8) Melanoma (5-8) UC (5-8) MSS CRC (5-8)
Expansion Cohort C-13	INCB059872, epacadostat and pembrolizumab beginning C1.	Biopsy #1 at baseline. Biopsy #2 during Week 5 or 6	HNSCC (5-8) Melanoma (5-8) UC (5-8) MSS CRC (5-8)

The sponsor will manage enrollment so that there are 5 to 8 evaluable subjects for a given tumor type. Subjects may be replaced if they have not completed all of the biopsy requirements.

3.1.4. Re-Treatment

3.1.4.1. Re-Treatment With Pembrolizumab or the Combination

Subjects who stop pembrolizumab or the combination with SD, PR, or CR may be eligible for up to an additional 17 cycles (approximately 1 year) of additional combination therapy or pembrolizumab if they experience disease progression after stopping the combination treatment or pembrolizumab. Re-treatment with pembrolizumab or the combination must be discussed and approved by the medical monitor. [REDACTED]

3.1.4.2. Re-Treatment With Azacitidine, INCB057643, or INCB059872

Re-treatment with azacitidine, INCB057643, or INCB059872 (based on original treatment assignment) along with pembrolizumab and epacadostat may be administered for subjects who had a CR, PR, or SD (for > 6 months) and later had evidence of PD while receiving pembrolizumab and epacadostat. Three additional cycles of azacitidine are permitted (for subjects originally enrolled in Treatment Group A). Cycle 1 Day 1 (or Day 1 of Week -1 for Expansion Cohort A-3) must be no more than 28 days after the subject has signed the ICF.

3.2. Randomization

Not applicable.

3.3. Control of Type I Error

For the primary efficacy endpoint in the Part 2 Simon 2-stage cohorts, the 1-sided Type I error will be controlled at 0.05 for each individual cohort expansion. For other endpoints, CIs will be reported at a 95% confidence level. Note that this level of significance does not account for the multiple expansion cohorts.

3.4. Sample Size Considerations

3.4.1. Sample Size in Part 1

3.4.1.1. Part 1 Dose Escalation

In Part 1, a 3 + 3 + 3 design will be used to assess the primary objective of determining the MTD, maximum tested dose, or PAD of the triplet combination of azacitidine, INCB057643, or INCB059872 with pembrolizumab and epacadostat in 21-day treatment cycles. Based on the 3 + 3 + 3 design algorithm, a minimum of 3 subjects and up to 9 subjects will be enrolled at each dose level. The total number of subjects will depend on the frequency of DLTs and number of dose levels tested before the MTD, maximum tested dose, or PAD is established.

3.4.1.2. Part 1 Dose Expansion

In addition to the dose-escalation cohorts, dose-expansion cohorts for Treatment Groups B and C in 5 NSCLC subjects who progressed on a PD-1 pathway-targeted agent and 5 MSS CRC subjects will be opened at each dose level tested that clears the DLT window for signal detection [REDACTED] analysis to guide an RP2D. See Sections 3.1.3.2.1 and 3.1.3.3.1 for Treatment Group B and C dose-expansion cohorts, respectively.

3.4.2. Sample Size in Part 2 Safety/Efficacy Expansion Cohorts

3.4.2.1. Part 2 Simon 2-Stage Cohorts

The safety/efficacy expansion in Part 2 will include 2 cohorts per treatment group, subjects with NSCLC who have had disease progression on a prior PD-1 pathway-targeted agent and subjects with MSS CRC. A Simon 2-stage design will be used for each of the cohorts (Simon 1989). The response rates for the historical control (p_0), desired response rates for the combination (p_1), number of subjects needed in Stage 1 (n_1) and Stage 2 (n_2), total number of subjects (n), first

stage threshold declaring cohort undesirable (r_1), and the upper limit of the number of responses in n subjects such that futility of the drug is concluded (r) are provided for each expansion cohort in [Table 10](#). The calculation is based on a 1-sided Type I error of 0.05 and power of 80%.

Table 10: Simon 2-Stage Design

Cohort	Tumor Type	p_0	p_1	n_1	n_2	n	r_1	r
Expansion Cohort A-1	NSCLC subjects who have had disease progression on a prior PD-1 pathway-targeted agent	3%	20%	8	19	27	0	2
Expansion Cohort A-2	MSS CRC	3%	20%	8	19	27	0	2
Expansion Cohort B-7	NSCLC subjects who have had disease progression on a prior PD-1 pathway-targeted agent	3%	20%	8	19	27	0	2
Expansion Cohort B-8	MSS CRC	3%	20%	8	19	27	0	2
Expansion Cohort C-9	NSCLC subjects who have had disease progression on a prior PD-1 pathway-targeted agent	3%	20%	8	19	27	0	2
Expansion Cohort C-10	MSS CRC	3%	20%	8	19	27	0	2

3.4.2.2. Part 2 Treatment Sequencing Tumor Biopsy Cohorts

Three treatment sequencing tumor biopsy cohorts per treatment group will be enrolled to evaluate epigenetic and tumor microenvironment changes. Five to 8 evaluable subjects per each tumor type will be enrolled in Expansion Cohorts A-3, A-4, B-9 through B-11, and C-11 through C-13. The eligible tumor types are HNSCC, melanoma, UC, and MSS CRC. Subjects with tumor types other than MSS CRC must have had disease progression on a prior PD-1 pathway-targeted agent. Ten subjects with first-line melanoma will be enrolled in Expansion Cohort A-5. See [Table 5](#), [Table 7](#), and [Table 9](#) for more details regarding treatment sequences and biopsy sequences for Treatment Groups A, B, and C, respectively.

Assuming the true rate of subjects positive for the biomarker is 70%, the probability of observing 16 or more subjects out of 25 subjects with the biomarker is 81% for Expansion Cohorts A-3, A-4, B-9 through B-11, and C-11 through C-13, and the probability of observing 6 or more subjects out of 10 subjects with the biomarker is 85% for Expansion Cohort A-5.

3.5. Schedule of Assessments

See Protocol Amendment 3 dated 20 OCT 2017 for a full description of all study procedures and assessment schedules for this study.

4. DATA HANDLING DEFINITIONS AND CONVENTIONS

4.1. General Considerations

Due to the early termination of the study, only subjects in Treatment Group A have been enrolled. No analyses on Treatment Groups B and C will be conducted.

4.2. Scheduled Study Evaluations and Study Periods

4.2.1. Day 1

For Expansion Group A-3, Day 1 is the date that the first dose of epacadostat or pembrolizumab is administered to subjects.

For all other treatment groups, Day 1 is the date that the first dose of any study drug (epacadostat, pembrolizumab, or azacitidine) is administered to subjects.

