Tumor biopsy/ tissue collection	X		X*			X**			* A second mandatory on-treatment biopsy will be collected prior to CID1 (window Day -5 to predose on CID1). **A third mandatory on-treatment biopsy will be collected during Week 5 or 6. Additional biopsies may be collected once the subject meets the requirements for SD, response, or progression by radiographic disease assessment. Detailed instructions for tissue collection, processing, and storage can be found in the study procedures manual. Fine needle aspirates are not acceptable.

Table 31: Schedule of Assessments (Treatment Group A: Part 2 Expansion Cohort A-3, Azacitidine Monotherapy Lead-In) (Continued)

Visit Day	Screening	Treatment					EOT	Safety Follow-Up	Notes
		Week -1	C1 D1	C2 D1	C2 D5-7	C3+ D1			
Evaluation Window	Day -28 to Day -1	C1D1-7 days	D1	± 3d	D5-7	±3 d	+ 5 d	EOT + 42-49 d	
STUDY DRUG ADMINISTRATION									
Administer azacitidine in clinic		X*		X**	X**	X**			* Five doses of azacitidine will be administered in the clinic over a 5- to 7-day period in Week -1 (before C1D1 of pembroliztunab/epacadostat). ** Azacitidine administration should continue with 5 doses administered in the clinic on D1-D7 of Cycles 2 and 3. Subjects who remain on treatment beyond the Week 9 scan should continue to receive azacitidine until the second on-study scan (up to the Week 18 scan, for a maximum of 3 additional cycles).
Administer epacadostat in clinic*			X**	X					* Subjects should withhold their AM dose of epacadostat on days. It should be administered in the clinic following the trough collection on C1D1 and C2D1. ** C1D1 treatment should be initiated within a + 5 day window from the date of the fifth azacitidine dose.
Administer pembroliztunab in clinic			X*	X		X			* C1D1 treatment should be initiated within a + 5 day window from the date of the fifth azacitidine dose.
EFFICACY ASSESSMENTS									
Radiologic tumor assessments*	X					X	X		* Every 9 weeks (63 ± 7 days) until disease progression. After 12 months of study treatment, imaging frequency may be reduced to every 12 weeks. Imaging should not be delayed for delays in cycle starts or extension of combination treatment cycle intervals.

Table 32: Laboratory Assessments (Treatment Group A: Part 2 Expansion Cohort A-3, Azacitidine Monotherapy Lead-In)

Laboratory Assessment Window	Screening	Week -1	Treatment				EOT	Safety	Notes
			C1	C2	C2	C3+			
			DI	DI	DS-7	DI			
	Day -28 to Day -1	C1D1 - 7 days	DI	±3 d	DS-7	±3 d	+Sd	EOT+ 42-49 d	

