7.6.1.2. Tumor Imaging During the Study

Tumor imaging may be performed by CT or MRI, but the same imaging technique should be used in a subject throughout the study. Scans must be a contrast CT or MRI, except in circumstances where there is a contrast allergy or with medical monitor approval. A PET/CT scan that uses higher energy and thinner slices for the CT component may be acceptable (with medical monitor approval) if it was the same technique used for baseline. Imaging should be performed every 9 weeks (63 days \pm 7 days) or more frequently if clinically indicated. After 12 months of study treatment, imaging frequency may be reduced to every 12 weeks. Imaging should not be delayed for delays in cycle starts or extension of combination treatment cycle intervals.

Imaging should continue to be performed until documented disease progression, the start of new anticancer treatment, withdrawal of consent, death, or the end of the study, whichever occurs first. Disease progression should be confirmed at least 4 weeks and not later than 8 weeks after the first scan indicating PD in clinically stable subjects. Subjects who have unconfirmed disease progression may continue on treatment until progression is confirmed provided that they have met the conditions detailed in Section 7.6.1.

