9. STATISTICS

9.1. Study Populations

The safety population includes all subjects enrolled in the study who received at least 1 dose of study drug (azacitidine, INCB057643, INCB059872, pembrolizumab, or epacadostat). All safety analyses will be based on the safety population.

The full analysis set includes all subjects enrolled in the study who received at least 1 dose of study drug (azacitidine, INCB057643, INCB059872, pembrolizumab, or epacadostat) and had at least 1 postbaseline assessment or discontinued treatment. All efficacy analyses will be based on the full analysis set.

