2.3.2. Secondary Endpoints

- Part 1: Objective response rate, defined as the percentage of subjects having a CR or PR, will be determined by investigator assessment of radiographic disease as per RECIST v1.1.
- Part 2: Safety and tolerability will be assessed by monitoring the frequency, duration, and severity of AEs; through physical examinations; by evaluating changes in vital signs and ECGs; and through clinical laboratory blood and urine sample evaluations.
- Parts 1 and 2: Percentage of responders, where a responder is defined as an increase in the number of TILs or the ratio of CD8+ lymphocytes to Tregs infiltrating tumor post-treatment versus pretreatment with pembrolizumab and epacadostat in combination with azacitidine, INCB057643, or INCB059872 evaluated by IHC, will be determined.

- Parts 1 and 2: Progression-free survival, defined as the time from date of first dose of study drug until the earliest date of disease progression, will be determined by investigator assessment of objective radiographic disease assessments per RECIST v1.1, or death due to any cause, if occurring sooner than progression.
- Parts 1 and 2: Duration of response determined by radiographic disease assessment, defined as the time from earliest date of disease response until the earliest date of disease progression as per RECIST v1.1, or death due to any cause, if occurring sooner than progression, will be determined.

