7.2.5. Progression-Free Survival

Progression-free survival will be assessed by RECIST v1.1.

[figure not shown]
Censoring for PFS will follow the algorithm outlined in [Table 12](#), which is based on the FDA Guidance for Industry: Clinical Trial Endpoints for the Approval of Cancer Drugs and Biologics ([FDA 2007](#)).

The KM estimate of median PFS will be presented with its 95% CI. The 95% CI will be calculated using Brookmeyer and Crowley's method (1982).

Table 12: Evaluation and Censoring of Progression-Free Survival

Situation	Outcome	Date of Progression or Censoring
No baseline tumor assessments	Censored	Date of Day 1
No valid postbaseline response assessments	Censored	Date of Day 1
Progression documented between scheduled response assessments	Progressed	Date of first overall response of PD
No progression	Censored	Date of last valid radiologic assessment (not NE and not missing)
Study discontinuation for undocumented progression	Censored	Date of last valid radiologic assessment (not NE and not missing)
Study discontinuation for toxicity or other reason	Censored	Date of last valid radiologic assessment (not NE and not missing)
New anticancer treatment started	Censored	Date of last valid radiologic assessment (not NE and not missing) on/before starting a new anticancer treatment.
Death before first progressive response assessment	Progressed	Date of death
Death between adequate response assessments	Progressed	Date of death
Death or progression after more than 1 missed assessment	Censored	Date of last valid radiologic assessment (not NE and not missing) prior to death

Under RECIST v1.1, PFS is defined as the length of time between the baseline visit (Day 1) and the earlier of death or first assessment of PD. Date of death will be determined using the Death Report, Survival Follow-Up, and Subject Status eCRFs.

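### For Cohort A-3 the SAP starts PFS about a week later than the PFS endpoint does, and leaves an azacitidine-only subject with no start date

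*SAP*

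**What the plan says.** The endpoint sections fix the PFS origin at first dosing. SAP 2.3.2 reads "Progression-free survival, defined as the time from date of first dose of study drug until the earliest date of disease progression", and the protocol synopsis and protocol 2.2.2 agree. Azacitidine counts as study drug: protocol 9.1 defines its populations by subjects who "received at least 1 dose of study drug (azacitidine, INCB057643, INCB059872, pembrolizumab, or epacadostat", and SAP 4.2.1, 4.2.3, 5.3.1 and 8.2.1 also name it.

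The SAP's analysis section uses a different anchor: "PFS is defined as the length of time between the baseline visit (Day 1) and the earlier of death or first assessment of PD". For A-3, SAP 4.2.1 defines that anchor as follows: "For Expansion Group A-3, Day 1 is the date that the first dose of epacadostat or pembrolizumab is administered to subjects". For all other groups, Day 1 is the first dose of any of the three drugs.

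In A-3 the first drug given is azacitidine alone. Protocol Table 31 states "Five doses of azacitidine will be administered in the clinic over a 5- to 7-day period in Week -1 (before C1D1", and the doublet follows: "C1D1 treatment should be initiated within a + 5 day window from the date of the fifth azacitidine dose".

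**The concern.** The Day 1 rule that makes sense for A-3 visit labels also sets the PFS clock, because 7.2.5 borrows the term. For A-3 alone, the clock then starts after a week or so of study treatment. The SAP's analysis of PFS no longer matches its own endpoint, and the shift always shortens PFS. Under the general rule in SAP 5.2, Group A data from Parts 1 and 2 are summarised together by dose level, so one Kaplan-Meier estimate would mix two time origins.

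There is also a gap. SAP 5.3.1 counts a subject as response evaluable after one azacitidine dose, a baseline scan and discontinuation of treatment, and Appendix A runs the PFS table on that population. An A-3 subject who stops during the lead-in qualifies but never reaches Day 1 as defined.

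**Working it through.** The plan states no figure for this offset, so there is none to reproduce. The check is date arithmetic plus a comparison of definitions.

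**Inputs**
- Protocol Table 31: five azacitidine doses over 5 to 7 days, all before C1D1; C1D1 within 5 days after the fifth dose; the Week -1 visit is nominally 7 days before C1D1.
- Protocol 7.6.1.2: scans every 63 days, with a window of 7 days either way. The documents do not say whether the A-3 scan schedule is counted from C1D1 or from the first azacitidine dose.

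**Offset between the two origins**
- First to fifth azacitidine dose: 5 − 1 = 4 days to 7 − 1 = 6 days.
- Fifth dose to C1D1: 1 to 5 days, taking the doses to precede C1D1 as Table 31 says.
- Total: 4 + 1 = 5 days to 6 + 5 = 11 days, nominally 7. If C1D1 could fall on the day of the fifth dose, the lower end would be 4.
- In months of 30.4375 days: 5/30.4375 = 0.16, 7/30.4375 = 0.23, 11/30.4375 = 0.36.

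**Relative size, scans counted from C1D1.** Shortening = offset / (scan day + offset).

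| Progression at | SAP PFS (days) | Endpoint PFS, nominal (range) | Shortening, nominal | Range |
|---|---|---|---|---|
| Scan 1 | 63 | 70 (68–74) | 7/70 = 10.0% | 5/68 = 7.4% to 11/74 = 14.9% |
| Scan 2 | 126 | 133 (131–137) | 7/133 = 5.3% | 5/131 = 3.8% to 11/137 = 8.0% |
| Scan 3 | 189 | 196 (194–200) | 7/196 = 3.6% | 5/194 = 2.6% to 11/200 = 5.5% |

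If scans are counted from the first azacitidine dose, the difference in days is the same. At scan 1 the shortening is then 7/63 = 11.1% (5/63 = 7.9% to 11/63 = 17.5%).

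**Definitions side by side, for A-3**
- SAP 7.2.5 calls Day 1 the baseline visit, but SAP 4.2.3 puts baseline before the first dose of any study drug. In A-3 these are different dates.
- SAP 7.2.2 counts the 56-day minimum for stable disease from the first dose of study drug. Stable disease and PFS would therefore run on different clocks in this cohort.

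**Azacitidine-only subject**
- The Table 12 row "No valid postbaseline response assessments" censors at Day 1, which does not exist for this subject. The study day in SAP 4.2.2 cannot be calculated either.
- A death or progression before C1D1 has an event date but no PFS start.
- A lead-in dropout with no postbaseline scan and no death would be censored at time zero under either origin. The missing Day 1 therefore alters a PFS result only for an event before C1D1.

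**The case against.** The strongest reply is that the later origin is intended. SAP 4.2.1 is an explicit, cohort-specific rule. Protocol 6.2 equates the first dose of study drug with Cycle 1 Day 1, and SAP 4.2.5 puts Cycle 1 Day 1 at the first pembrolizumab dose. The PFS objective concerns the combinations, so starting the clock when the combination starts is a reasonable choice after a monotherapy lead-in.

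Part of this stands: the rule suits visit alignment, and a combination-start clock could be defended if it were the stated endpoint. It is not. Protocol 6.1 and 6.2 name Day 1 of Week -1 separately for A-3, so the general gloss in 6.2 does not describe this cohort. Azacitidine is listed as a study drug throughout, and SAP 7.2.2 still counts from first dose.

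It is also fair to say that the 7-day scan window is as wide as the nominal offset. But the window runs in both directions, while the offset always shortens PFS. The 5-day allowance for C1D1 appears in the current protocol (Tables 5 and 31) and not in the SAP's own Table 5, so the upper end of the range rests on the protocol.

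**Conclusion.** The inconsistency is real and minor. As written, A-3 PFS times not censored at time zero are 5 to 11 days (nominally 7) too short against the endpoint, and a lead-in death or progression has no PFS start. PFS is secondary and descriptive, no decision rule uses it, and one cohort is affected. About 25 subjects were planned for A-3. Actual enrolment after the early stop, and whether anyone received azacitidine only, are not given. The percentages assume on-schedule dosing and scans.

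Four stronger readings are tempting but not supported:
- **That both Table 12 rows censoring at Day 1 fail.** The row for subjects without baseline tumour assessments cannot apply here, because SAP 5.3.1 requires a completed baseline scan. Only the row for no valid postbaseline assessment is affected.
- **That PFS is generally shortened by 7% to 17%.** Those figures hold only for progression at the first scan, and the proportion falls with each later one.
- **That the SAP changed the PFS origin without declaring it.** The visible part of SAP 10.1 lists no such change, but 10.1.1 is partly redacted and 10.1.2 is not shown, so this cannot be established.
- **That the medication-date rules in SAP 4.2.4 are also wrong because they refer to Day 1.** No resulting error has been shown.

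**What to change.** In SAP 7.2.5, and in the Table 12 entries that censor at Day 1, use the date of first dose of any study drug (azacitidine, pembrolizumab or epacadostat) for all cohorts. Keep the A-3 Day 1 convention in 4.2.1 for study-day and visit labelling only. Add a fallback there: for an A-3 subject who never receives epacadostat or pembrolizumab, Day 1 is the first dose of any study drug. Leave 4.2.4 as it is.

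The cost is a few lines of SAP text and one derived variable. Dosing dates are already collected, and nothing changes at the sites.
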